#### 9.10. Other Aspects

Not applicable.

#### 10. PROTECTION OF HUMAN SUBJECTS

#### 10.1. Patient Information

This study will involve data that will exist in anonymized structured format and contain no personal patient information.

#### 10.2. Patient Consent

As this study will involve anonymized structured data, which according to applicable legal requirements do not contain data subject to privacy laws, obtaining informed consent from patients will not be required.

## 10.3. Institutional Review Board (IRB)/Independent Ethics Committee

The study protocol will be submitted to the local IRB to apply for an exemption/waiver from IRB review prior to data transfer.

All correspondence with the local IRB will be retained and copies of correspondence filed in accordance with good pharmacoepidemiology practices (GPP).

#### 10.4. Ethical Conduct of the Study

The study will be conducted in accordance with legal and regulatory requirements, as well as with scientific purpose, value, and rigor, and will follow generally accepted research practices described in Guidelines for GPP issued by the International Society for Pharmacoepidemiology, Good Practices for Outcomes Research issued by the International Society for Pharmacoeconomics and Outcomes Research (ISPOR), and United States Food and Drug Administration Guidance for Industry: Good Pharmacovigilance and Pharmacoepidemiologic Assessment.

# 11. MANAGEMENT AND REPORTING OF ADVERSE EVENTS/ADVERSE REACTIONS

This study involves data that exist as structured data by the time of study start or a combination of existing structured data and unstructured data, which will be converted to structured form during the implementation of the protocol solely by a computer using automated/algorithmic methods, such as natural language processing. In these data sources, individual patient data are not retrieved or validated, and it is not possible to link (ie, identify a potential association between) a particular product and medical event for any individual. Thus, the minimum criteria for reporting an adverse event (AE) (ie, identifiable patient, identifiable reporter, a suspect product, and event) cannot be met.

#### 12. PLANS FOR DISSEMINATING AND COMMUNICATING STUDY RESULTS

The results of this study will be made public by posting on clinicaltrials.gov. Further communication of these data may occur via abstracts and manuscripts.

## ANNEX 1. LIST OF STAND ALONE DOCUMENTS

Number	Document reference number	Date	Title
1	Section 4	09 January 2023	Real-World Effectiveness of Tafamidis 80 mg or 61 mg on Neurologic Disease Progression in Patients with Mixed- Phenotype ATTRv-CM

#### ANNEX 2. ENCEPP CHECKLIST FOR STUDY PROTOCOLS

Not required.

## ANNEX 3. ADDITIONAL INFORMATION

Not applicable.

# 1. AMENDMENTS FROM PREVIOUS VERSION(S)

Not applicable.

#### 2. INTRODUCTION

ATTR amyloidosis is a progressive, life-threatening, and heterogeneous rare disease caused by the deposition of transthyretin-derived amyloid fibrils in the peripheral nerves, heart, and other organs.  ATTR amyloidosis may arise from mutations in the transthyretin (TTR) gene (ATTRv amyloidosis), with more than 140 ATTRv genotypes having been identified,  or from the aggregation of non-mutated wild-type TTR (ATTRwt amyloidosis). Amyloid deposition in the peripheral nerves results in transthyretin amyloid polyneuropathy (ATTR-PN). Multiple symptoms and system involvement are hallmarks of ATTR-PN. Amyloid fibril deposition in the extracellular matrix of the heart results in ATTR-CM, and is characterized by arrhythmias and heart failure.  ATTRwt amyloidosis predominantly manifests as ATTR-CM. ATTRv amyloidosis is now widely recognized as a spectrum of disease that can manifest as polyneuropathy, cardiomyopathy, or a mixed phenotype, depending on the particular TTR variant, amyloid deposition pattern, and multisystem involvement.

Tafamidis meglumine is a first-in-class highly specific and selective stabilizer for both wild-type and amyloidogenic variants of transthyretin (TTR) developed for the treatment of ATTR amyloidosis.

Tafamidis meglumine 20 mg was the first disease-modifying therapy approved for the treatment of ATTR-PN and is currently labeled and approved for once-daily dosing for treatment of transthyretin amyloidosis in adult patients with stage 1 symptomatic polyneuropathy to delay peripheral neurologic impairment. It is available in over 40 countries worldwide (excluding the United States) and marketed as VYNDAQEL, tafamidis meglumine 20 mg for treating ATTR-PN.

Likewise, tafamidis delivered as either VYNDAQEL 80 mg (four 20-mg tafamidis meglumine capsules) orally once daily or VYNDAMAX 61 mg (one 61-mg tafamidis capsule) orally once daily was the first disease-modifying therapy approved for the treatment of cardiomyopathy of wild-type or hereditary transthyretin-mediated amyloidosis in adults to reduce cardiovascular mortality and cardiovascular-related hospitalization. Tafamidis is currently approved for the treatment of ATTR-CM in approximately 46 countries worldwide (including the United States).

While the safety and efficacy of VYNDAQEL has been demonstrated by clinical studies for AATR-PN and ATTR-CN, neurologic endpoints were not evaluated in the ATTR-CM development program. Therefore, there is a need to assess the potential benefit of tafamidis, as either VYNDAQEL 80 mg (four 20-mg tafamidis meglumine capsules) orally once daily or VYNDAMAX 61 mg (one 61-mg tafamidis capsule) orally once daily for delaying neurologic disease progression in ATTR amyloidosis. To address this knowledge gap, this

observational study will use secondary data to examine neurologic disease progression among patients with ATTRv-CM treated in the real-world setting.

## 2.1. Study Design

This will be an observational, retrospective cohort study using structured secondary anonymized data. Patients with mixed-phenotype ATTRv-CM receiving tafamidis, as either VYNDAQEL 80 mg (four 20-mg tafamidis meglumine capsules) orally once daily or VYNDAMAX 61 mg (one 61-mg tafamidis capsule) orally once daily for at least 6 months, will be identified. Relevant data will be extracted through at least 6 months following the initiation of tafamidis treatment (with a ±3-month window).

The index date of this study is defined as the date of tafamidis treatment initiation with at least 6-month (and up to 12 months) pre-index period as the study pre-treatment baseline. Patients will be followed from index date for at least 6 months post-treatment (with a  $\pm 3$ -month window).

This study also includes three assessment windows in which the study endpoints will be extracted and evaluated. The pre-treatment assessment will be extracted at least 6 (and up to 12 months) prior to treatment initiation. The tafamidis initiation assessment will be obtained 3 months before or 3 months after the start of tafamidis treatment. The post-treatment endpoints will be assessed at least 6 months after (with a  $\pm 3$ -month window) treatment initiation.

The final study design will be determined based on feasibility assessment.

[figure not shown]

Figure 1. Overview of Study Design

\*Charcot-Marie-Tooth neuropathy score v2 (CMTNS2); mBMI: Modified body mass index; MRC: Medical Research Council; NIS-CS: Neuropathy impairment score-composite score; NIS-LL: Neuropathy impairment score-lower limbs; PND: Polyneuropathy disability.

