#### 9.2.1. Inclusion Criteria

Patients must meet all the following inclusion criteria to be eligible for inclusion in the study:

- 1. Age ≥18 years at diagnosis.
- 2. Diagnosed with ATTRv-CM, mixed phenotype.
- 3. Treated with tafamidis (VYNDAQEL 80 mg [four 20-mg tafamidis meglumine capsules] orally once daily or VYNDAMAX 61 mg [one 61-mg tafamidis capsule] orally once daily) for ≥6 months.
- 4. Have had ≥1 pre- and ≥1 post-treatment neurologic assessments.\*

\*The pre-treatment neurological assessment will be at least 6 and up to 12 months prior to treatment initiation. The baseline assessment will be within 3 months before or 3 months after the start of tafamidis treatment. In the absence of baseline data within a+/-3 month window, structured data from exam notes may also be retrieved if available to align with real world practice. The post-treatment period will be at least 6months after treatment initiation.

Note: As this study involves anonymized structured data, which according to applicable legal requirements do not contain data subject to privacy laws, obtaining informed consent from patients is not required.

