# Inclusion criteria

- Age ≥18 years at diagnosis
- Diagnosed with hereditary ATTR-CM, mixed phenotype
- Treated with tafamidis (VYNDAQEL 80 mg [four 20-mg tafamidis meglumine capsules] orally once daily or VYNDAMAX 61 mg [one 61-mg tafamidis capsule] orally once daily) for ≥6 months (with a ± 3-month window)
- Have had ≥1 pre- and ≥2 post-treatment neurologic assessments\*+

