# 7.1.3. Analyses for Change from Baseline and Repeated Measured Endpoints

Continuous variables representing neurologic disease progression, such as NIS-CS, NIS-LL, PND, MRC, CMTNS2 and mBMI may be collected at multiple time points. Measures may be reported in the pre-treatment baseline period (at least 6 months (and up to 12 months) before treatment initiation), tafamidis initiation (within 3 months before or after treatment initiation), and post-treatment (at least 6 months after treatment initiation with a ±3-month window) as population mean, SD, median, first and third quartiles, and range in a table or chart format. If a participant had multiple values in one or more of the pre-defined periods, the mean value will be used in calculating the population-level summary statistics. More details of the number of assessments and assessment schedule will be finalized once the data structure is known.

PND and CMTNS2 scores will be summarized using a frequency table for both the pre-treatment and tafamidis treatment periods. Additionally, a shift table will be used to capture the change in PND and CMTNS2 scores between the two periods. The shift table will capture the changes at each visit relative to start of the period, ie, baseline for the pre-treatment period and tafamidis initiation visit for the tafamidis treatment period (within 3 months before or after treatment initiation).

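### Untreated assessments between 6 and 3 months before tafamidis start fall in no assessment window, so they can go unused and some patients can drop out of the pre/post comparison

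*SAP*

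**What the plan says.** SAP 2.1 names three windows in which endpoints are extracted and evaluated.

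- Pre-treatment: "The pre-treatment assessment will be extracted at least 6 (and up to 12 months) prior to treatment initiation". The protocol footnote to inclusion criterion 4 (9.2.1) agrees: "The pre-treatment neurological assessment will be at least 6 and up to 12 months prior to treatment initiation".
- Initiation: "The tafamidis initiation assessment will be obtained 3 months before or 3 months after the start of tafamidis treatment". The protocol has the same window and calls it baseline.
- Post-treatment: SAP 7.1.3 has "post-treatment (at least 6 months after treatment initiation with a ±3-month window"; the protocol footnote has no such tolerance: "The post-treatment period will be at least 6months after treatment initiation".

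Criterion 4 also differs. The protocol has "Have had ≥1 pre- and ≥1 post-treatment neurologic assessments"; the SAP's inclusion list has "Have had ≥1 pre- and ≥2 post-treatment neurologic assessments".

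There is a fallback for a missing baseline. The protocol footnote says: "In the absence of baseline data within a+/-3 month window, structured data from exam notes may also be retrieved if available". Footnotes to protocol Table 9-3 and SAP Table 2 similarly allow baseline data from outside ±3 months.

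SAP 7.2 plans a linear mixed model with time in months. It needs at least three assessments per patient: one pre-treatment, one on treatment and one more in either period. If too few patients qualify, the SAP turns to an unpaired t-test or to separate analyses by number of assessments.

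**The concern.** The first window ends at −6 months and the second begins at −3, and neither document says what happens to an assessment in between. A value at −7 or −2 months is used and one at −4 is not, and no reason is given.

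Two things are at stake. First, an untreated value that would inform the pre-treatment slope may never be extracted, although the model could place it at its actual month. Second, the footnote ties criterion 4 to the −12 to −6 window, so a patient whose one untreated assessment falls at −4 months is ineligible because of visit timing. The reason given for Amendment 1 is that most patients are not expected to have multiple measures before or after treatment. If a patient has only one untreated assessment, its date decides whether the patient is in the comparison.

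**Working it through.** **Inputs.** Windows from SAP 2.1 and 7.1.3 and the protocol 9.2.1 footnote. The SAP's post-treatment start is 6 − 3 = +3 months; the protocol's is +6.

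**Classification of assessment times (months from start).**

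| Time | SAP | Protocol |
|---|---|---|
| −12 to −6 | pre-treatment | pre-treatment |
| strictly between −6 and −3 | none | none |
| −3 to before +3 | initiation | initiation |
| exactly +3 | initiation and post-treatment | initiation |
| strictly between +3 and +6 | post-treatment | none |
| +6 and later | post-treatment | post-treatment |

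**Length of the gap.** 6 − 3 = 3 months. That is 3/12 = 25% of the year before start, or 3/9 = 33% of the span from −12 to −3. These are shares of calendar time, not of patients.

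**Consequences for individual patients (constructed examples).**

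- Assessments at −9, −4, 0 and +8: the value at −4 has no period. Month 0 supplies the initiation value, so the fallback does not apply and −4 is unused. The patient still has three assessments.
- Assessments at −9, −4 and +8: −4 may be taken as a substitute baseline. The SAP does not say whether a substitute counts toward the three-assessment minimum. If it does not, only two remain.
- Assessments at −4, +1 and +8: nothing lies in −12 to −6, so criterion 4 fails. The fallback supplies a baseline, not the required pre-treatment assessment. SAP 7.2 gives such patients descriptive statistics only.

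**Number affected.** It cannot be computed, because the documents give no distribution of assessment times. There is also no sample size calculation to reproduce, only the estimate of at least 30 patients.

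**Illustration of what a loss would cost.** The loss fractions are assumptions. For the SAP's unpaired fallback comparison (two-sided alpha 0.05, 80% power, normal approximation), the detectable difference in SD units is d = (1.960 + 0.842) × √(2/n):

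| Assumed loss from 30 | n | d | Power at 0.5 SD |
|---|---|---|---|
| 0% | 30 | 0.72 | 49% |
| 10% | 27 | 0.76 | 45% |
| 25% | 22.5 | 0.84 | 39% |
| 33% | 20 | 0.89 | 35% |

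This shows sensitivity to loss only. It does not estimate the loss.

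**The case against.** The case for leaving the windows alone has several parts.

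- *A 6-month minimum is defensible in a progression study.* This stands. A patient with a single untreated value at −4 months has little or no untreated slope, and the fallback t-test ignores elapsed time, so relaxing criterion 4 would mix unequal intervals. A reader might infer that the criterion is an error; the documents do not show that.
- *Gap values are not always lost.* This stands in part. A reader might infer that every such value is discarded, but one may serve as baseline when none lies within ±3 months. It does not become the required pre-treatment assessment, and it is unused when an in-window baseline exists.
- *The mixed model may not be bound by the windows.* SAP 7.2 speaks of two periods and continuous time, and SAP 2.1 also describes a pre-index period 6 to 12 months long, which could be read as running up to start. But SAP 2.1 says endpoints are extracted in the windows. The text is at best ambiguous.
- *The design is not final.* SAP 2.1 and 7.1.3 defer details to feasibility and data structure. But feasibility was due to be complete on 30 October 2022, and the protocol of 31 May 2023 still has the gap.

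Two further readings go too far. One is that the overlap at +3 months loses data: it is a single boundary point, arises only under the SAP, and assigns a treated value twice. The other is a stated share of patients lost. Any such figure needs a visit interval and a candidate count, and the documents give neither.

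**Conclusion.** The gap from −6 to −3 months is present in both documents. Untreated assessments in it go unused unless taken as a substitute baseline, and a patient with no other untreated assessment leaves the pre/post comparison. The size in patients is unknown and could be nil: the estimate of at least 30 may already count only those who fit the windows. The conclusion assumes that extraction follows the windows as SAP 2.1 states. The case for change is that it is cheap: the values are usable in a model with time in months, would add precision to the untreated slope, and can help patients reach three assessments.

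Of minor weight, and separate: the SAP has no tie rule at exactly +3 months; the protocol leaves +3 to +6 months unassigned where the SAP does not; and the two differ on one versus two post-treatment assessments. SAP 4.1 defines the analysis set by the protocol's criteria while the SAP lists different ones, so these passages must be reconciled.

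**What to change.** 1. In SAP 2.1 and 7.2, state that every dated assessment from 12 months before start onward is extracted, enters the mixed model at its actual month, belongs to the pre-treatment period if before first dose and to the treatment period if after, and counts toward the three-assessment minimum. Add one rule for an assessment on the first-dose date.
2. For summary tables, use contiguous, exclusive windows, identical in both documents: pre-treatment −12 to before −3; initiation −3 to +3 inclusive; post-treatment after +3, or as reconciled with the protocol.
3. Reconcile the post-treatment start and the required number of post-treatment assessments.
4. Keep criterion 4's pre-treatment limit for the main analysis. As a sensitivity analysis, add patients whose only untreated assessment lies between −6 and −3 months, with time zero at that assessment.
5. Report how many patients and assessments fall outside the current windows.

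Cost: SAP wording, a matching protocol footnote and slightly more extraction from the existing database. Some patients will contribute shorter, noisier untreated intervals.

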## 2.1.1. Study Population

The study will include patients with mixed-phenotype ATTRv-CM who are treated with tafamidis, as either VYNDAQEL 80 mg (four 20-mg tafamidis meglumine capsules) orally once daily or VYNDAMAX 61 mg (one 61-mg tafamidis capsule) orally once daily. All patients meeting the study enrollment criteria will be included.

# Inclusion criteria

- Age ≥18 years at diagnosis
- Diagnosed with hereditary ATTR-CM, mixed phenotype
- Treated with tafamidis (VYNDAQEL 80 mg [four 20-mg tafamidis meglumine capsules] orally once daily or VYNDAMAX 61 mg [one 61-mg tafamidis capsule] orally once daily) for ≥6 months (with a ± 3-month window)
- Have had ≥1 pre- and ≥2 post-treatment neurologic assessments\*+

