#### 4. ANALYSIS SETS/POPULATIONS

#### 4.1. Full Analysis Set

The study will include all patients with mixed-phenotype ATTRv-CM who meet the study protocol I/E criteria and are treated with tafamidis, as either VYNDAQEL 80 mg (four 20-mg tafamidis meglumine capsules) orally once daily or VYNDAMAX 61 mg (one 61-mg tafamidis capsule) orally once daily for at least 6 months (with a ±3-month window). All patients meeting the below study enrollment criteria will be included in the full analysis dataset. It is estimated that at least 30 patients will be included in the analysis.

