#### 7.2. Statistical Analyses

For the primary and secondary objectives, neurologic function, ie, NIS-CS, NIS-LL, MRC, CMTNS2, and mBMI will be examined in the full analysis set. If there is a sufficient number of patients with at least three neurologic assessments a linear mixed-effect model will be conducted to compare the rate of disease progression (within patient) between pre-treatment and tafamidis treatment periods. Patients must have at least three assessments to be included in the linear mixed-effect model (one in the pre-treatment period, one in the tafamidis treatment period, and one additional that can be in either pre-treatment or in the tafamidis treatment period). The linear mixed-effect model includes pre-treatment baseline score, treatment period, and their interactions with time as fixed effects, and the time-slope and intercept for each patient are included as random effects. Time is defined as number of months from pre-treatment baseline. The estimates of the monthly rate of change, along with the 95% confidence interval and the p value associated with the within group comparison comparing the pre-treatment and tafamidis treatment periods will be summarized.

However, if there is not a sufficient number of patients with at least three neurologic assessments, and many patients only have two assessments, then an approach is to take the first measurement and the measurement that fell within the window of the measurement in which majority of the patients had for the post-treatment assessment (whether they only have two or three or more) and test for significant statistical differences between the two assessments using an unpaired, or independent samples, t-test.

Alternatively, in the event there is an insufficient number of patients with three or more neurologic assessments, separate subgroup statistical analyses may be performed. This approach may use a between-subjects analysis of variance (ANOVA) for patients with at least three neurologic assessments and conduct unpaired, or independent samples, t-test for

patients with only two neurologic assessments. Descriptive summaries will be provided by treatment (pre-treatment or post-treatment), or by subgroups (if data permits) for each neurologic function endpoint.

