It is anticipated that there will be patients who do not satisfy inclusion criteria for pre and post treatment comparisons for various reasons such as not being on treatment for at least 6 months (with ±3-month window) because they passed away, not having a pre-treatment or post-treatment neurologic assessment, not having a NIS score or other missing data points and/or reasons. While pre and post treatment comparisons cannot be conducted for these patients, descriptive statistics on the composite score and/or its sub-scale will be reported to characterize patient and treatment characteristics.

Additional post-hoc analyses of final data from this study may be performed against final data from comparable tafamidis-treated and untreated ATTRv mixed phenotype patients from the Transthyretin Amyloidosis Outcomes Survey (THAOS; Pfizer Study B3461001). If performed, analysis methods will be provided as part of an amendment to this SAP.

All data analysis will be executed using statistical software SAS version 9.4.

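### SAP 2.1.1 requires two post-treatment assessments where Protocol 9.2.1 requires one, and so would exclude patients whom SAP 7.2 plans to analyse

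*SAP*

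**What the plan says.** **Eligibility.** Protocol 9.2.1, criterion 4: "Have had ≥1 pre- and ≥1 post-treatment neurologic assessments". SAP 2.1.1, the same criterion: "Have had ≥1 pre- and ≥2 post-treatment neurologic assessments". Both are current text.

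**Analysis set.** SAP 4.1 takes patients "who meet the study protocol I/E criteria and are treated with tafamidis". It then adds "All patients meeting the below study enrollment criteria will be included in the full analysis dataset", but no list follows in that section; the only list in the SAP is the earlier one in 2.1.1.

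**Analysis.** SAP 7.2 works in the full analysis set. Its mixed model needs three assessments: one pre-treatment, one on tafamidis, and "one additional that can be in either pre-treatment or in the tafamidis treatment period". If too few patients have three and "many patients only have two assessments", it falls back to a t-test on two measurements. An alternative gives patients with exactly two assessments their own t-test. Among the reasons why a patient may be ineligible for the pre/post comparison it names "not having a pre-treatment or post-treatment neurologic assessment".

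**Initiation visit.** SAP 2.1 sets a third window, within 3 months either side of treatment start. SAP 7.1.3 starts the on-treatment period at the "tafamidis initiation visit for the tafamidis treatment period".

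**Treatment duration.** SAP 2.1.1, 4.1 and 7.2 attach a ±3-month window to the 6-month treatment minimum. Protocol 9.2.1 and the first statement of the minimum in SAP 2.1 do not.

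**The concern.** Who enters the full analysis set depends on whether the programmer follows the list in SAP 2.1.1 or the protocol criteria named in SAP 4.1. If the SAP list is applied, patients with one post-treatment assessment lose the primary pre/post comparison. Under the last part of SAP 7.2 they would only be described. Yet the same section sets out analyses for exactly these patients.

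Protocol 9.7 lets the SAP modify the protocol's plans, but nothing in the SAP presents the higher count as a deliberate change, and SAP 4.1 points back to the protocol.

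As context only: the log for protocol Amendment 2 records a change from ≥2 to ≥1 in criterion 4 as a typographical correction, without saying which of the two counts was meant. The SAP wording may therefore be an uncorrected remnant. The conflict does not depend on that log, since it lies between the two current texts.

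**Working it through.** There is no sample-size calculation to reproduce; Protocol 9.5 says none was done. The check is a count of which patients each rule admits.

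**Minimum assessments per patient**

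- Protocol 9.2.1: 1 + 1 = 2.
- SAP 2.1.1: 1 + 2 = 3. It stays 3 however the initiation visit is classed, provided no visit is counted twice.

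**Patterns.** Write each patient as (pre, initiation, post). Take at least one pre, at least one post, and at most three in total.

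| Pattern | Protocol 9.2.1 | SAP 2.1.1, initiation not post-treatment | SAP 2.1.1, initiation counted as post-treatment | Place in SAP 7.2 |
|---|---|---|---|---|
| (1,0,1) | yes | no | no | two-assessment t-test |
| (2,0,1) | yes | no | no | mixed model |
| (1,1,1) | yes | no | yes | mixed model |
| (1,0,2) | yes | yes | yes | mixed model |
| Admitted | 4 of 4 | 1 of 4 | 2 of 4 | all 4 have a planned analysis |

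**Wider range.** The cap of three is a choice, so the count was repeated for 1 to 3 pre and 1 to 3 post assessments without a separate initiation visit, giving 3 × 3 = 9 patterns. The protocol admits 9. The SAP list admits 6, losing 1/1, 2/1 and 3/1, which are all the patterns with exactly one post-treatment assessment. SAP 7.2 covers all 9: eight have three or more assessments and meet the mixed-model rule, and 1/1 goes to the t-test.

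**Effect on the two-assessment branch.** Every patient admitted by SAP 2.1.1 has at least three assessments. The branch for two could then arise almost only where a visit took place but a particular scale was not recorded.

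**Effect on precision, illustration only.** The share of patients with one post-treatment assessment is not given. Assume that 30 patients meet the protocol criterion, and let the share *s* vary. The 95% confidence half-width for a mean change, in SD units, is t(0.975, n−1)/√n.

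| Assumed *s* | Patients left | Half-width | Ratio to n = 30 |
|---|---|---|---|
| 0 | 30 | 0.373 | 1.00 |
| 10% | 27 | 0.396 | 1.06 |
| 25% | 22 | 0.443 | 1.19 |
| 50% | 15 | 0.554 | 1.48 |
| 75% | 8 | 0.836 | 2.24 |

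Losses of 7.5 and 22.5 patients were taken as 8 and 22. The log for protocol Amendment 1 says that repeated measures on either side of treatment start were not expected for most patients. That suggests *s* may not be small, but gives no figure.

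**The case against.** Several points can be made on the other side.

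- **SAP 4.1 already follows the protocol.** It names the protocol criteria and states no count of its own. On that reading the SAP list removes nobody. This is why the loss is stated as conditional. But the next sentence of 4.1 points to a list that is not there, and the only list in the SAP carries the higher count.
- **The pattern fractions are not patient fractions.** This stands. They are unweighted and move with the cap: 1 or 2 of 4 with at most three assessments, 6 of 9 in the wider count. What does not move is the minimum of two against three, and the loss of patients with exactly one post-treatment assessment and no initiation visit.
- **The two-assessment branch is not strictly empty.** This also stands. The criterion counts assessments, not scales, and the NIS totals are computed only where the data allow. The first fallback t-test also takes in patients with three or more. Even so, the condition that triggers it is that many patients have only two.
- **The ineligibility examples in SAP 7.2 are open-ended.** Correct; they support the protocol's count only weakly.
- **The SAP criterion carries two footnote marks whose text is not in the copy reviewed.** The footnotes might define post-treatment. Both obvious readings were tested, and (1,0,1) and (2,0,1) fail under each.
- **The study is exploratory.** SAP 3.1 says so. That lowers the stakes of any single p-value, but not the need for one rule on who is analysed.

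**Conclusion.** The concern holds. The two current documents set different minimum counts, two against three, and the SAP is inconsistent with itself on which applies. If SAP 2.1.1 is applied as written, patients with one pre- and one post-treatment assessment leave the full analysis set. So do those with two pre, one post and no initiation visit. SAP 7.2 plans an analysis for both groups. Patients with one assessment in each of the three windows stay or go depending on how the initiation visit is classed.

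The number lost cannot be computed from the documents. The conclusion rests on the criterion as it reads without its footnotes, and on no visit being counted twice. It must be corrected because it decides membership of the set used for the primary objective. The difference over the ±3-month window is a secondary inconsistency whose effect the documents do not state.

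**What to change.** 1. In SAP 2.1.1, set the criterion to at least one pre- and at least one post-treatment assessment, as in Protocol 9.2.1.
2. In SAP 4.1, replace the pointer to a list below with a cross-reference to that single list.
3. State whether an assessment in the initiation window counts as pre-treatment, post-treatment or neither. The corrected count alone leaves this open.
4. Reconcile the minimum-treatment statements in Protocol 9.2.1 and SAP 2.1, 2.1.1, 4.1 and 7.2 so that one rule applies. No figure is proposed here.

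If the higher count was intended, the SAP should say so as a change from the protocol, and 4.1 and 7.2 must be rewritten to match.

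The cost is one number, one cross-reference and a sentence or two in the SAP. A short protocol amendment is needed only if the protocol's duration wording is the text that changes. No new data are required.
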